24 APRIL 2019

Date

ADDENDUM #1

Section 1.0

Add the following text after the first paragraph:

Pre-Unblinding SAP modifications and extensions are specified based on realization of a need for clarification of the SAP, recognition of additional useful sensitivity and challenge analyses, a need to conform to precedents set by other similar studies, and a need to facilitate the understanding of results from this study in the context of other contemporary similar studies. The study remains blinded as this addendum is written. The primary statistical criteria are not changed as a result of this addendum.

The details of AESIs, concomitant medications of interest, treatment effect on non-melanoma and melanoma precursors are added as a separate document.

Note: This trial is double blind and therefore the following considerations apply to the time when the data can be unblinded. An unblinded analysis based on a January 1, 2019 cutoff and an April 25, 2019 soft lock will be prepared for a highly selected distribution. Immediately after release of the randomization file (consisting of two main items: patient identifier and actual assigned arm) this file will be sent to the consulting statistician. Following this transmission, and during the time when the final analysis SDTM datasets are being validated, the consulting statistician will use a merge of this randomization file with the blinded datasets already in possession of the consulting statistician to refine the study presentation slides working together with selected others. (The results are expected to be close to the final results.) The study presentation will be finalized after the validated SDTM datasets are sent to the consulting statistician.

Section 4.1

Delete the following sentence at the end of the first paragraph:

The primary efficacy analysis will be based on the ITT analysis.

Add the following text to the end of the first paragraph:

The ITT analysis set is to be considered as all patients randomized without regard to having initiated study intervention and free of pre-randomization findings of not meeting inclusion/exclusion criteria and not randomized in error, the existence of which must be discovered based on post-randomization review of data collected pre-randomization.

The analysis set used for the primary analysis will be a modified ITT analysis set and will be referred to as the Full Analysis Set (FAS). The FAS is the terminology preferred in ICH Topic E9 and is the ITT analysis set with deletion of patients not initiating study intervention. The FAS is unbiased in the sense that the ITT analysis set is unbiased because this study is blinded. Analyses based on the ITT analysis set become sensitivity analyses. The rationale for this change is to conform to previously published similar

studies, the very low frequency of deletions from the ITT analysis set to create the FAS, and changes in the perception of the status of RFS relative to patient benefit.

Section 6.9.1

Add the following text in the Table where “randd” is defined:

The randomization date is that from the IVRS system.

Add the following text in the Table where “strat” is defined:

The stage used as a stratification factor in the primary analysis and related analyses is that collected from the IVRS system.

Add the following text after the paragraph before and in the Box providing template code for use of the LIFETEST and PHREG procedures:

When using SAS PROC LIFETEST quantile confidence intervals will be computed using the option CONFTYPE=LINEAR in order to invoke the Brookmeyer-Crowley method. When using PROC PHREG use the option TIES=EXACT.

Section 6.9.2

Add the following text after the first paragraph:

RFS Variable: The following variables play a role in the ascertainment of recurrence and is used for the primary analysis of recurrence as well as the recurrence sensitivity analysis to be described subsequently:

1. *The first assessment date for each patient is to be the date of randomization.*
2. *In dataset CE, variable CEOCUR (and its associated date) flags a suspicious finding on the associated date.*
3. *In dataset FA, variable FAORRES for the code variable FATESTCD with values ABCT, CHESTCT, CHESTX, and PCT are missing if not reported or flag negative (N) or positive (Y) finding for the respective radiological findings on the associated date.*
4. *In dataset FA variable FAORRES for code BMRI is missing if a brain MRI is not reported or flag negative (N) and positive (Y) brain MRI finding on the associated date.*
5. *In dataset FA variable FAORRES for code BIOPSY is missing if not reported or flag negative (N) or positive (Y) biopsy finding on the associated date.*
6. *In dataset FA variable FAORRES for code CONFIRM is missing if not reported or flag negative (N) or positive (Y) confirmation of a suspicion (see above) on the associated date, which should be a date with a suspicion flag on the same date.*

Note: A brain MRI or biopsy positive finding may not induce a confirmation of a suspicion.

7. *A recurrence is indicated for the date of a first confirmation, brain MRI, or biopsy positive finding. Note: A positive brain MRI finding does not require a biopsy, whereas a radiological or other suspicious finding (physical exam, for example) does require a positive biopsy though this check does not need to be coded. Therefore, there may be exceptions so a confirmation without any other positive finding is technically possible. Also note: A recurrence should always be associated with a suspicion, but not all suspicions will be confirmed.*
8. *Assessment modalities such as radiology are involved only as an auditing aids and play no role in detecting the presence of recurrence.*
9. *For endpoints with censoring based on date last known alive:*
 - a. *If censor date is after the cutoff date then the censor date should be adjusted to the cutoff date.*
 - b. *If event date is after the cutoff then change the event to a censor on cutoff date.*
10. *For endpoints with censoring based on assessment date:*
 - a. *If censor date is after the cutoff date then adjust censor date to previous assessment.*
 - b. *If date of event is after the cutoff then change the patient to being censored of the previous assessment date.*

Add the following text in the Table where “randd” is defined:

The randomization date is that from the IVRS system.

Add the following text in the Table where “strat” is defined:

The stage used as a stratification factor in the primary analysis and related analyses is that collected from the IVRS system.

Replace the text in the Table for the definition of “rdi” with the following text/definition:

The definition of rdi is specified prior to this table as one of the created from RFS variables.

Replace the text in the Table for the definition of “rdd” with the following text/definition:

The definition of rdd is specified prior to this table as one of the created from RFS variables. The value of rdd is the date last known alive for a patient without recurrence or death.

Add the following text after the paragraph before and in the Box providing template code for use of the LIFETEST and PHREG procedures:

When using SAS PROC LIFETEST quantile confidence intervals will be computed using the option CONFTYPE=LINEAR in order to invoke the Brookmeyer-Crowley method. When using PROC PHREG use the option TIES=EXACT.

Section 6.9.3.2

Add the following text as a bullet point after the first two bullet points in the first paragraph:

An RFS sensitivity analysis with the event defined as the date of recurrence or if there is no observed recurrence then date of death up to 120 days since last recurrence assessment. Censoring for this analysis will be the date of last recurrence assessment.

[End of Addendum #1]

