6.2.2 Subject Withdrawal from Recurrence Assessments

Even in the case of termination of study intervention, subjects will be encouraged to continue to attend follow-up assessments as outlined in Section 5.

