9.3 Part B Clinical Efficacy Parameters

Survival time is computed based on the date of death if the subject is known dead or the date last known to be alive (censored). Zero time for a subject is the date of randomization.

Recurrence-free survival time (RFS) is computed from the earliest of the date of recurrence or death or, if without recurrence or death, the date last assessed for recurrence without a diagnosis of recurrence (censored). The date of recurrence is specified as the first date a recurrence is suspected, which is later confirmed by biopsy. In the rare cases where biopsies are not clinically appropriate (e.g., brain metastases), the recurrence date will be set by the treating clinician's medical judgment. Zero time for a subject is the date of randomization.

Recurrence will be monitored through tumor imaging (as specified in Section 9.3.1) every 6 months until recurrence, death, subject withdrawal, early termination or completion of the study.

LDH is also monitored every 3 months for early indication of possible recurrence. LDH elevations of 1.5 X ULN (or greater) will be followed up with radiological scans, provided there are no other obvious medical reasons for the elevated LDH.

Recurrence is defined as the occurrence of the following events:

- Loco-regional relapse
- Distant metastasis
- A new melanoma that is likely unrelated to the original primary lesion

Investigators are required to obtain biopsies of recurrent tumors to provide pathologic evidence of recurrence unless the recurrence is in the brain. In the case of multiple lesions during an imaging examination, biopsy of at least one lesion should be obtained.

As the determination of recurrence will primarily rely on biopsies, there will be no central reading of CT scans to confirm recurrence.

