Key analyses may depend on the date of the first occurrence of an event associated with the endpoint. When the event has yet to occur the analysis will nonetheless require an analytical date be available for the analysis. These are known as censored or truncated dates. A censored date is the date of the most recent assessment for the event for a patient for which the event of interest has yet to occur and for which additional time may lead to observation of the event of interest. A truncated date is the date of a

competing event that precludes the observation of the event of interest. The distinction between designating an analytical date as censored or truncated will depend on the purpose of the analysis and will be designated for each analysis. For example, if death is the event of interest and a patient is still alive and being followed for the date of death then the date last known alive is a censored date, whereas the date a patient withdraws consent for continued follow-up of vital status (a competing event) is a truncated date. Please note that the nature of the competing event will dictate whether the competing event is permanent. For example, the date of death for a patient who has withdrawn consent may later become known passively from governmental death records.

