The primary analysis will consist of executing two SAS procedures, a stratified log-rank test for the test of the hypothesis and a proportional hazard regression to estimate the hazard ratio and its 95% confidence interval.

```
proc lifetest;
  strata strat / group=expi test=logrank;
  time rdt*rdi(0,-1);
run;

proc phreg;
  class strat;
  strata strat;
  model rdt*rdi(0,-1)=expi / rl ties=exact;
run;
```

The significance of the logrank test will be assessed by referring the one-sided stratified logrank test P value to the significance criterion applicable to the analysis. The one-sided stratified logrank test P value, P_1 , is to be computed as follows from the hazard ratio estimate from the proportional hazard regression, HR, and the two-sided P value from stratified logrank test, P_2 : If $HR < 1$ then $P_1 = P_2/2$. If $HR \geq 1$ then $P_1 = 1 - P_2/2$.

Notes:

- These analyses must be stratified (3).
- When there are competing events then censoring competing events provides a between-arm test of the event of interest (4).

The RFS data will be plotted as either Kaplan-Meier or cumulative incidence distribution estimate depending on the amount of competing events. The cumulative incidence estimates and not the Kaplan-Meier estimates will be plotted if the percent of patients with competing events in either arm exceeds 10%. (When there are competing events then the Kaplan-Meier estimate is not an estimate of the probability free of event (5)).

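### Addendum #1 censors primary RFS at the date last known alive, Protocol 9.3 at the last recurrence assessment; one primary date is needed, with both rules reported

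*SAP*

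**What the plan says.** Protocol 9.3 computes RFS to recurrence or death or, failing both, to "the date last assessed for recurrence without a diagnosis of recurrence (censored"). SAP 4.6 gives a general definition that points the same way: "A censored date is the date of the most recent assessment for the event".

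Addendum #1 (24 April 2019) replaces the rdd cell in SAP 6.9.2 and adds: "The value of rdd is the date last known alive for a patient without recurrence or death". For the event indicator it says: "The definition of rdi is specified prior to this table as one of the created from RFS variables". The list before the table has ten items. Items 1 to 8 describe how a recurrence is ascertained. Items 9 and 10 give cutoff rules for endpoints censored at the date last known alive and for endpoints censored at an assessment date.

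The model code in SAP 6.9.2 still reads "time rdt*rdi(0,-1"), so it expects codes 0 and -1.

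The addendum adds one RFS sensitivity analysis to SAP 6.9.3.2. It censors at the last recurrence assessment and counts a death only within 120 days of that assessment.

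**The concern.** RFS is the sole primary endpoint of Part B1 and one of two in Part B2, yet the current documents give two censoring dates for it. A programmer following the addendum and one following the protocol would build different time variables from the same data.

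The difference matters for a patient who stops recurrence assessment, remains known alive and is not a competing event. Under the addendum that patient stays in the risk set as recurrence-free through time in which recurrence was not looked for. A later death still counts. Such patients can exist: after treatment stops, Protocol 6.2.2 says only that "subjects will be encouraged to continue to attend follow-up assessments", while under 6.2.3 vital-status follow-up ends only at the subject's request.

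The addendum is also incomplete. None of its ten items names rdi or rdd, says what -1 means, or says whether item 9 or item 10 governs RFS. It gives a specific reason for changing the primary analysis set ("The rationale for this change is to conform to previously published similar" studies, among others). The censoring change has only the general preamble, which could cover it.

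**Working it through.** **Which texts are current.** The addendum edits SAP 1.0, 4.1, 6.9.1, 6.9.2 and 6.9.3.2 only. Protocol 9.3 and SAP 4.6 therefore stand. The replaced rdd cell of SAP 6.9.2 is superseded and is not used here.

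**The plan's own figure.** SAP 5.2.1 gives 126 events and 80.5% simulated power for Part B1. Simulating the delayed-effect model of SAP Appendix 3 (2:1, three strata, 10,000 replicates) gives 82.1% power and a one-sided alpha of 0.101, within 2 points. Neither censoring rule changes the event target or alpha. Both use the same events and differ only in time at risk.

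**Inputs from the documents.** 325 patients, 2:1. Control RFS rates are 0.154, 0.198 and 0.409 per year in a 30.9/30.4/38.7% mix (SAP 5.2.1). Accrual runs from January 2015 to about June 2016 and the cutoff is January 1, 2019, so follow-up is 2.5 to 4.0 years.

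True 2.5-year RFS = 0.309·exp(−0.154×2.5) + 0.304·exp(−0.198×2.5) + 0.387·exp(−0.409×2.5) = 0.210 + 0.185 + 0.139 = 0.535 after rounding.

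**Assumptions, not in the documents.** No vaccine effect. Stopping of assessment is exponential and independent of recurrence. Deaths occur only after recurrence, at 0.35 per year. Every stopper is known alive until death or cutoff. Recurrences are dated exactly. There is no competing-event censoring. At stopping rates c of 4, 8 and 12% a year, the share who stop before recurrence and cutoff is the stage-weighted mean of c/(c+λ)·[1−exp(−(c+λ)u)] over u from 2.5 to 4.0 years: 8%, 16% and 22%.

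**Results**, with the rejection rate of the one-sided 0.10 test where given:

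| Stopping per year, vaccine / placebo | Recurrences recorded after stopping | Last known alive | Last assessment, all later events counted |
|---|---|---|---|
| 0 / 0 | not applicable | no bias, HR 1.00 | no bias, HR 1.00 |
| 8% / 8% | none | RFS about +2.8 points, HR 1.00 | RFS about −0.4, HR 1.00 |
| 8% / 8% | half | 54.9% (+1.4), HR 1.00 | 52.1% (−1.4), HR 1.00 |
| 12% / 4% | none | HR 0.91, rejects about 25% | HR about 1.02 |
| 12% / 4% | half | HR 0.95 to 0.96, rejects about 16% | HR about 1.05 |
| 4% / 12% | none | HR 1.09, rejects about 4% | HR about 0.98 |
| 8% / 6% | none | HR 0.98, rejects about 12% | HR about 1.01 |

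With equal stopping at any rate run, the test rejects about 10 to 11% of the time, as it does with no stopping.

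**Sensitivity to the assumptions.** With none recorded after stopping and 8% a year in both arms, the overstatement is about 1.5 points if only half of stoppers keep vital status to cutoff, and 3.3 points if all do and recurrences are dated at 6-monthly assessments. At 12% against 4%, with half keeping vital status, HR is 0.94 to 0.95 and rejection 18%.

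**The 120-day analysis.** It changes the censoring date and the death rule together, so it does not isolate the censoring change. With 6-monthly assessments it overstates RFS by 1.5 points even with no stopping, because 120 days is shorter than the assessment interval. HR stays at 1.00.

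**The case against.** The strongest reply is that the primary test is a stratified logrank comparison, and equal stopping leaves it alone. The trial is double blind, and the documents give no basis for a threefold difference in stopping. This stands. Under equal stopping, what moves is the height of the Kaplan-Meier curves, which is not the success criterion.

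The rule may also be deliberate. It was written while the study was blinded, and item 9 for primary RFS with item 10 for the 120-day analysis is a coherent reading. SAP 4.6 is a softer conflict than Protocol 9.3: it is a general definition, its own example censors death at the date last known alive, and RFS includes death. The meaning of -1 can be recovered from the competing-event paragraph left in SAP 6.9.2. All of this is fair, but Protocol 9.3 still names a different date.

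The exposed group is limited. Protocol 5.2.11 and 6.2.1 press for continued assessment, separate survival contact is described only after recurrence (5.2.10), and definite loss and consent withdrawal are competing events. SAP 6.9.3.2 already promises alternative censoring analyses, though it does not name this one.

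A reader might infer two stronger points. The first is that the addendum contradicts itself, since it states: "The primary statistical criteria are not changed as a result of this addendum". That phrase can refer to significance levels and event targets, and the same addendum openly changes the primary analysis set, so no contradiction is shown. The second is that last-assessment censoring is nearly unbiased. That holds only if almost no recurrence is recorded after assessment stops. The documents do not confine recurrence to scheduled imaging: Protocol 9.3 dates it from first suspicion, and item 7 of the addendum names physical examination as a source of suspicion.

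**Conclusion.** The conflict is certain: the addendum and Protocol 9.3 give different censoring dates for the primary endpoint, and the definitions to which the addendum points are absent. It should be reconciled.

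The size is assumption only. Under the model above, at 8% a year equal stopping, the addendum's rule overstates 2.5-year RFS by about 2.8 points if no later recurrence is recorded and by about 1.4 if half are. In the second case the protocol's rule errs by about 1.4 points the other way. The hazard ratio shifts only if stopping differs by arm, in either direction.

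The documents do not support saying that the Part B1 test is invalid or its type I error inflated, or that one rule is right and the other wrong in every setting. The protocol's rule is preferred as primary because it is the protocol's definition. The two rules are best read together.

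**What to change.** In Addendum Section 6.9.2, restore the Protocol 9.3 rule and define the variables in full:

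- rdi = 1: rdd is the date of recurrence or death.
- rdi = 0: rdd is the last recurrence assessment on or before the cutoff.
- rdi = -1: rdd is the competing-event date.

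State that item 10 applies to RFS and item 9 to overall survival. Report last-known-alive censoring as a named RFS sensitivity analysis with the same events and the same death rule, so that the two results bracket the effect of the choice. Keep the 120-day analysis beside them, but not as an unbiased reference. Tabulate by arm the number of patients who stop assessment while known alive; that count shows whether the choice matters.

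The cost is addendum wording, one derivation line and one table. It needs no new data and no change to alpha, events or sample size. There is slightly less follow-up time and a small downward bias in RFS. At 8% a year equal stopping the bias is about 0.4 points if only deaths after missed assessments are counted, and about 1.4 if half of the later recurrences are counted too.
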